5.2 Secondary Objectives

- Comparison between the speech reception thresholds in the OLSA test in noise across all audio processors and audio processor settings.
- Comparison between the speech reception in quiet (Freiburg Monosyllables Test) across all audio processors and audio processor settings.
- Comparison of subjective user satisfaction, sound quality, quality of hearing, and listening effort across audio processors and audio processor settings

5.3 Study Outcome Measures

5.3.1 Primary outcome measures

The primary outcome measure is speech intelligibility in the S0N0 set-up in the OLSA speech test in noise. For a description of the test setup see Section 10.2.3

5.3.2 Secondary outcome measures

Performance of the SONNET 2 will be assessed with different combinations of frontend processing features under different environmental test conditions using the following tests:

- Speech performance
 - ❖ Freiburg Monosyllabic test in quiet; speech presented from the front
 - ❖ Oldenburg Sentence Test in noise in the set-ups
 - S0N0
 - S0N0T0
 - S0, ±N45, ± N135
- Quality of hearing in real life
 - ❖ HISQUI19

- ❖ SSQ12
- Device handling
 - ❖ Data Logging
 - ❖ APSQ
- Subjective Rating
 - ❖ ACALES
 - ❖ Subjective Sound Quality Rating
 - ❖ Product Specific questionnaire

6 HYPOTHESES

6.1 Hypotheses for the Primary Objectives

The primary objective of this study is to show non-inferiority of SONNET2 in a OLSA in noise speech test (S0N0) compared to the SONNET. The margin of non-inferiority is set to 2 dB SNR (Hey, Hocke, Hedderich, & Müller-Deile, 2014; Nogueira, Rode, & Buchner, 2016).

- Verbal formulation

Hypothesis H_0 (Null Hypothesis):

Speech perception with the SONNET 2 in its default setting in the OLSA in noise (S0N0) is inferior to the speech perception in the same test condition with the SONNET.

Hypothesis H_1 (Alternative Hypothesis):

Speech perception with the SONNET 2 in its default setting in the OLSA in noise (S0N0) is non-inferior to the speech perception in the same test condition with the SONNET.

- Mathematical formulation

$$H_0: \mu_1 - \mu_2 \geq \Delta \text{ (2 dB SNR)}$$

$$H_1: \mu_1 - \mu_2 < \Delta \text{ (2 dB SNR)}$$

Where:

μ_1 = SONNET mean OLSA in noise (S0N0) results for the study population expressed in dB SNR

μ_2 = SONNET2 mean OLSA in noise (S0N0) results for the study population expressed in dB SNR

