Early CI development aiming at enhancing speech recognition, have focused on increasing number of channels and the stimulation rate and improving the signal-processing strategies and the electrode design. Considerable improvements were also reached by improved front-end processing methods. MED-EL cochlear implants incorporate the Automatic Sound Management (ASM). This technology provides a wide input dynamic range and to some extent protection from sudden loud sound to cochlear implant users which is achieved by a dual loop automatic volume control and automatic gain control. Additionally, dual, omni-directional or adaptive directional microphones, and remote microphone technologies can improve signal quality by optimizing the acoustic signal. In combination with pre-processing algorithms, the signal can be enhanced for different environments, for instance by automatically identifying sounds, and thus customized for the individual user. A common approach is to use two omni-directional microphones to form fixed or adaptive directional microphones, also known as beamforming. With the SONNET, MED-EL introduced ASM 2.0 including wind-noise reduction and microphone directionality and significant improvements in speech performance could be shown (Hagen et al., In submission). With the most recent audio processor, SONNET 2, ASM 3.0 including new front-end features were incorporated: the noise reduction, the transient noise reduction and an automatic scene classifier.

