10.2 Tests/Material

10.2.1 Impedance Field Telemetry (IFT)

A telemetry recording will be performed according to the procedures explained in the MED-EL Fitting Guide. The impedance field telemetry (IFT) recording ensures the proper function of the implant and measures impedances on all electrodes as well as the ground path.

These data form the basis of every clinical map and are necessary to interpret differences between fitting maps.

10.2.2 **Speech testing in quiet**

The Freiburg Monosyllabic test is an open-set monosyllabic word test and is widely used to test adults in German-speaking countries (K.-H. Hahlbrock & Zöllner, 1970; K. H. Hahlbrock, 1970). It consists in total of 20 lists with 20 words each. Each patient shall perform a training starting the actual testing. The results scored in this training session will not be analysed. The test lists will be allocated according to a randomization procedure. The analysis evaluates the number of correctly repeated words in % correct at a fixed presentation level. Speech is presented at 65dB SPL. The test shall be performed in quiet.

10.2.3 **Speech testing in noise**

In this study speech audiometry in noise will be performed using Oldenburger matrix sentence tests (Wagener, Brand, & Kollmeier, 1999a, 1999b; Wagener, Kühnel, & Kollmeier, 1999).

Oldenburger matrix sentence tests are available as measurement modules of the Oldenburger Measurement Application (OMA) (Hörtech GmbH). Matrix sentence tests will be used in the study, due to the sensitivity and applicability in a two-language study. Speech audiometry with the Oldenburger matrix sentence test using speech test material in the national language of the study site.

The test is used to assess the 50% speech-recognition threshold (SRT50 in dB SNR), which is a measure of the level difference at which speech can be identified at half the time in presence of simultaneous masking noise.

The sentences of matrix tests all are composed with the same structure. Test lists with 20 or 30 items are generated from several such sentences. The words are taken in a seemingly random fashion from an inventory (a matrix) of 50 words (10 words per category).

10.2.4 **Subjective user ratings**

10.2.4.1 **Audio Processor Satisfaction Questionnaire (APSQ)**

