11.5.2 Speech testing

11.5.2.1 *Freiburg Monosyllables*

The Freiburg Monosyllables in quiet will be implemented according to the routine testing approach at the study centre. The results are recorded and expressed in % correct and reported in the CRFs.

11.5.2.2 **OLSA**

The Oldenburger Matrix Sentence Test will be performed according to the specification in the case report form (e.g. order of configuration etc.). Prior to the test lists, a training round will be performed at each visit. Noise level will be fixed to 60 dB SPL and the speech level will be adaptive.

The OLSA will be performed in different set-ups (also see Figure 1):

- S0N0

Speech and noise signal are both presented from the front of the subject (0° angle).

- S0N0T0

Speech, noise and transient noise are presented from the front of the subject (0° angle).

- S0, $\pm 45^\circ$, $\pm 135^\circ$

Speech is presented from the loudspeaker in front of the subject (0° angle). Stationary noise presented from +45° and -45° angle and +135° and -135° angle.

[figure not shown]

Figure 1 Loudspeaker set-up

11.5.3 **Subjective user ratings**

11.5.3.1 **Audio Processor Satisfaction Questionnaire (APSQ)**

The APSQ will be completed by the subject. An instruction is given in the questionnaire document. These data are considered source data.

11.5.3.2 ***Hearing Implant Sound Quality Index 19 (HISQUI19)***

The HISQUI will be completed by the subject. An instruction is given in the questionnaire document. These data are considered source data.

11.5.3.3 ***SSQ12 (Speech Spatial Qualities) in German***

The SSQ12 will be completed by the subject. An instruction is given in the questionnaire document. These data are considered source data.

11.5.3.4 ***SONNET 2 questionnaire***

The SONNET 2 Questionnaire will be completed by the subject. An instruction is given in the questionnaire document. These data are considered source data.

11.5.3.5 ***Subjective rating***

11.5.3.6 ***ACALES Test***

To evaluate the listening effort induced by different configurations, the ACALES test will be performed. In this test, the subject will listen different sound files and rate the subjectively perceived listening effort on a scale from “effortless” to “extremely effortful”. Depending on the rating of the subject, the level of the signal will be varied adaptively while the noise level is kept constant,

The ACALES will be performed in different set-ups (also see Figure 1):

- S0N0

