7.6.2 Speech testing in noise

The OLSA test is used to assess the speech-recognition threshold for 80% correct word recognition in noise (SRT80 in dB SNR). The noise level is fixed, and the speech level is adaptive.

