8 SAMPLE SIZE

The primary objective of this study is to show non-inferiority of SONNET2 in a OLSA in noise speech test (S0N0) compared to the SONNET. The margin of non-inferiority is set to 2 dB SNR.

Comparable data of the final report "Performance of Cochlear Implant Patients with Microphone Directionality and Wind Noise Reduction with the "SONNET" of the OLSA in noise speech test (S0N0) were used as basis for the sample size calculation:

OPUS2	mean: 0.589 dB;	± SD: 1.586 dB vs.
SONNET natural-MILD	mean: -0.088 dB;	± SD: 1.463 dB

The sample size was estimated using the formula on noninferiority (Chow, Shao et al. 2008):

$$N = (1 + \frac{1}{r})(\sigma \frac{Z_{crit} + Z_{pwr}}{(\mu_A - \mu_B) - \Delta})^2$$

Assuming a non-inferiority margin of 2 dB (Δ), with an alpha-level of 0.025 (noninferiority, one-sided) and a power of 90%, a minimum sample size of 13 subjects was calculated (Z_{crit} is the normal quantile for the 0.025 alpha level, and Z_{pwr} is the normal quantile for the 90% power). To allow for possible dropouts (approximately 20%) and to provide additional safety and efficacy data, a maximum of 30 subjects will be included in this study.

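### The printed primary hypotheses run opposite to their wording: on a threshold where lower is better, H1 holds however much worse SONNET 2 is

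*Protocol*

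**What the plan says.** Protocol 6.1 states the primary hypotheses in words and in symbols. In words, the null is "Speech perception with the SONNET 2 in its default setting in the OLSA in noise (S0N0) is inferior to the speech perception" with the SONNET, and the alternative is that SONNET 2 is non-inferior. In symbols, H0 is mu1 - mu2 at or above 2 dB, and the alternative is "H_1: \mu_1 - \mu_2 < \Delta \text{ (2 dB SNR". The first mean, mu1, is defined as "SONNET mean OLSA in noise (S0N0) results for the study population expressed in dB SNR"; mu2 is the corresponding mean for SONNET 2. SAP 9.1 repeats the same inequalities and the same assignment of mu1 and mu2. It adds sentences about a 2 dB mean difference that carry no sign.

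On the scale of the outcome, Protocol 10.2.3 says "The test is used to assess the 50% speech-recognition threshold (SRT50 in dB SNR"), and Protocol 11.5.2.2 says "Noise level will be fixed to 60 dB SPL and the speech level will be adaptive". SAP 7.6.2 names an 80% threshold instead, but on the direction it agrees: "The noise level is fixed, and the speech level is adaptive".

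SAP 11.2.1 calculates the mean difference between the two processors with a 95% confidence interval and asks whether that difference is below 2 dB. Protocol 15.1.1 refers to a difference smaller than 2 dB and then names a t-test or Wilcoxon signed-rank test for a significant difference.

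**The concern.** The outcome is the signal-to-noise ratio a subject needs to reach a fixed level of recognition. A higher value means that louder speech was needed, which is worse. A non-inferiority margin must therefore cap SONNET 2 minus SONNET. The printed inequality caps SONNET minus SONNET 2, which limits how much better SONNET 2 may be and leaves harm unlimited.

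The hypothesis symbols are the only place where an order of subtraction appears with its labels defined. The sample size formula in Protocol 7.3 and SAP 8 contains mu_A - mu_B, but A and B are not identified. An analyst who implements the symbols, or a reviewer who validates the analysis against them under SAP 17, would be carrying out or endorsing a test that cannot detect inferiority. SAP 3 says the plan exists to prevent post hoc decisions. The direction of the primary test would be such a decision, in an open-label study analysed by the sponsor's statistician.

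**Working it through.** **The plan's own sample size.** Inputs from Protocol 7.3 and SAP 8: SDs of 1.586 dB (OPUS 2) and 1.463 dB (SONNET), a 2 dB margin, and a design "with an alpha-level of 0.025 (noninferiority, one-sided) and a power of 90"%. The pooled SD is sqrt((1.586² + 1.463²)/2) = 1.526. With r = 1 and a true difference of zero, the printed formula gives

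N = 2 × (1.526 × (1.960 + 1.282) / 2)² = 12.2, which rounds up to the stated 13.

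The tabulated difference of 0.677 dB does not reproduce 13: it gives 28 if taken towards the margin and 7 if taken away from it. The figure of 13 therefore implies a planning difference of zero. The formula is then symmetric in sign, so the sample size neither reveals the intended direction nor depends on it.

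**Direction of the scale.** No single sentence says that lower is better, but three things agree.
- The outcome is a threshold with fixed noise and adaptive speech.
- Protocol 3.1 contrasts cochlear implant users with normal-hearing people by the higher ratios they need, +5 to +20 dB.
- The planning means are 0.589 dB for the older OPUS 2 and -0.088 dB for the newer SONNET. Protocol 3.1 cites the same source for "microphone directionality and significant improvements in speech performance could be shown". Older minus newer is 0.589 - (-0.088) = +0.677 dB when the newer device is better.

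The hypotheses use the same order, older minus newer, so a positive mu1 - mu2 favours SONNET 2.

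**Algebra.** Let w be the amount in dB by which SONNET 2 is worse, so mu1 - mu2 = -w.
- Printed H1: -w < 2, that is w > -2. This is true for every harm, however large.
- Printed H0: -w ≥ 2, that is w ≤ -2. This is true only if SONNET 2 is at least 2 dB better.

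This step needs no assumption about variance or sample size.

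**SAP 11.2.1.** Read in the order in which it names the processors (SONNET, then SONNET 2), it repeats the error. Read as SONNET 2 minus SONNET with the upper limit compared with 2 dB, it is right. The text does not choose between these readings.

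**Size.** The rule applied is that the upper limit of the two-sided 95% interval must be below 2 dB, with a paired t interval. The probability of declaring non-inferiority is

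P(T < -t(0.975, n-1)), where T is noncentral t with n-1 degrees of freedom and noncentrality (m - 2)/(SD_d/√n),

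with m = -w under the printed order and m = +w under the corrected order.

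The documents give no within-subject correlation, so 0, 0.5 and 0.8 are assumed. From SD_d = sqrt(1.586² + 1.463² - 2 × rho × 1.586 × 1.463), these give 2.158, 1.528 and 0.971 dB.

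Example with n = 13, correlation 0.5 and w = 2: SD_d/√n = 1.528/√13 = 0.424. The noncentrality is -4/0.424 = -9.4 under the printed order and 0 under the corrected order.

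Results at n = 13 for correlations 0 / 0.5 / 0.8:

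| True state | Printed order | Corrected order |
|---|---|---|
| SONNET 2 better by 2 dB | 2.5% at all three | >99.9% at all three |
| Equal | 86.5% / 99.1% / about 100% | the same |
| SONNET 2 worse by 2 dB | >99.9% at all three | 2.5% at all three |
| SONNET 2 worse by 3 dB | about 100% at all three | at most 0.02% |
| SONNET 2 worse by 5 dB | 100% at all three | 0% |

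At the maximum of 30 subjects, the row for 2 dB worse is again about 100% against 2.5% at all three correlations.

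**The case against.** The strongest reply is that the intent is plain. Both documents repeatedly state in words that SONNET 2 is to be shown non-inferior to SONNET, so an analyst would have to ignore all of that to follow the symbols. On this view it is a label swap, and a signed difference reported with its confidence interval would let any reader apply the right limit afterwards. This is largely true. It explains why the repair is simple and why no data would be lost. It does not make the pre-specified rule correct, because the plan's only labelled order of subtraction is the wrong one and the analysis section does not override it.

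A second reply is that results for harms inside the margin say little about this defect. At n = 13 the corrected rule passes a device that is 1 dB worse in 58.3% of trials at correlation 0.5; at n = 30 it does so in 93.4%. The difference reflects power, and a correct test should often pass such a device. That stands, so the case here rests on harms at or beyond 2 dB, where sample size and correlation make no practical difference.

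A third reply is that following the words does not give a complete test either. Protocol 5.1 compares two configurations of SONNET 2, whereas Protocol 6.1 compares SONNET 2 with SONNET, and the documents disagree on the 50% or 80% threshold. Those conflicts are real but separate. Neither changes the direction of the scale.

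**Conclusion.** The concern holds. In both documents the mathematical primary hypotheses contradict the verbal ones, and the printed alternative is true for any degree of SONNET 2 harm. SAP 11.2.1 leaves the direction open. At a true deficit equal to the margin, the printed rule would declare non-inferiority almost always (above 99.9%), where the design allows 2.5%; at a true benefit of 2 dB the two figures are exchanged. The contradiction itself follows from the definitions alone. The probabilities rest on a paired t interval, the planning SDs and an assumed correlation, but the contrast at 2 dB is the same at correlations of 0, 0.5 and 0.8 and at 13 or 30 subjects. This must be fixed because it concerns the trial's only confirmatory test, although it is evidently a sign or label error and not a flaw of intent.

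**What to change.** In Protocol 6.1 and SAP 9.1, write H0: mu(SONNET 2) - mu(SONNET) ≥ 2 dB and H1: mu(SONNET 2) - mu(SONNET) < 2 dB.

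In SAP 11.2.1, state that the difference is SONNET 2 minus SONNET, paired within subject, and that non-inferiority is concluded if the upper limit of the two-sided 95% confidence interval is below +2 dB. This matches the one-sided 0.025 level used for the sample size.

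Align Protocol 15.1.1 with that rule, because a test for a significant difference does not by itself establish non-inferiority.

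The cost is wording in four sections. No new data or subjects are needed, and the minimum of 13 stands because it was derived at zero true difference. The processor configurations being compared and the threshold level should be reconciled separately, so that the corrected rule refers to one defined comparison.

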6.2 Hypotheses for the Secondary Objectives

The secondary objectives of this study are to provide additional evidence on the performance of SONNET 2-specific front-end features. Thus, the analyses are of an explorative nature and will not influence the results of the primary outcome of the study. Due to the exploratory nature of the secondary objectives, no hypothesis is formulated a priori.

7 STUDY DESIGN

7.1 Type of Study

This study has been planned as a mono-centric, open label, prospective longitudinal study where each subject acts as his/her own control.

The SONNET 2 is an incremental innovation to the SONNET audio processor with additional front-end processing features which are designed to improve patient performance in specific auditory environments. The study is designed to prospectively follow-up experienced SONNET users who received the SONNET 2. As intra-individual control, subjects will be acutely tested with the SONNET in the same test conditions as with the SONNET 2.

7.2 Study Population

This study will be performed with experienced users of MED-EL cochlear implants (defined as a minimum experience of 6 months with a MED-EL cochlear implant and their current audio processor) who will be followed-up for five study specific visits to the test centre.

7.3 Sample Size Calculation

The primary objective of this study is to show non-inferiority of SONNET2 in a OLSA in noise speech test (S0N0) compared to the SONNET. The margin of non-inferiority is set to 2 dB SNR (Hey et al., 2014; Nogueira et al., 2016).

Comparable data of the final report "Performance of Cochlear Implant Patients with Microphone Directionality and Wind Noise Reduction with the "SONNET" of the OLSA in noise speech test (S0N0) were used as basis for the sample size calculation (Hagen et al., In submission):

OPUS2	mean: 0.589 dB;	± SD: 1.586 dB vs.
SONNET natural-MILD	mean: -0.088 dB;	± SD: 1.463 dB

The sample size was estimated using the formula on noninferiority (Chow, Shao, & Wang, 2008):

$$N = (1 + \frac{1}{r})(\sigma \frac{Z_{crit} + Z_{pwr}}{(\mu_A - \mu_B) - \Delta})^2$$

Assuming a non-inferiority margin of 2 dB (Δ), with an alpha-level of 0.025 (noninferiority, one-sided) and a power of 90%, a minimum sample size of 13 subjects was calculated (Z_{crit} is the normal quantile for the 0.025 alpha level, and Z_{pwr} is the normal quantile for the 90%

power). To allow for possible dropouts (approximately 20%) and to provide additional safety and efficacy data, a maximum of 30 subjects will be included in this study.

7.4 Duration of the Study

Subject enrolment is scheduled to last for 15 months. If the minimum number of subjects is not achieved, enrolment may continue until the minimum number of subjects is reached or for an additional 9 months.

7.5 Management of Deviations from the CIP

Investigational sites shall inform the Monitor immediately about any deviations as they become aware of them. In addition, compliance to the CIP is verified by the Sponsor through monitoring sessions according to the study Monitoring Plan provisions.

Deviations that potentially affect the study outcome are recorded and listed in the final Clinical Investigation Report.

7.6 Protocol Amendments

Major Amendments shall be submitted to the relevant IEC(s) and NCA(s). Amendments may be implemented only after IEC(s) and, if required, NCA(s) approval has been obtained.

Amendments that are intended to eliminate an apparent immediate hazard for the subjects enrolled in the study may be implemented prior to receiving the relevant IEC(s) approval. However, in this case, approval shall be obtained as soon as possible after implementation.

No changes in the study procedures shall be affected without the mutual agreement of MED-EL, the Investigator and the Coordinating Investigator (if applicable). All changes shall be documented in the form of signed protocol amendments, or as a revised protocol. Changes to the protocol may require notification to or approval by the relevant IEC(s) before implementation. Local regulatory requirements shall be followed.

The Monitor is responsible for the distribution of protocol amendment(s) to the Investigator(s) and those concerned within the conduct of the study. The Investigator is responsible for the distribution of all amendments to the staff involved at his centre.

8 STUDY ENROLMENT AND WITHDRAWAL

8.1 Selection Criteria

8.1.1 Inclusion criteria

- A minimum of 18 years old
- Experienced user (\geq 6 months) of a MED-EL cochlear implant (C40+ and later model)
- Experienced user of a MED-EL SONNET audio processor (\geq 6 months)
- Post-lingual onset of bilateral severe to profound sensory-neural hearing loss
- Unilateral CI user
- A minimum of 10 active electrodes
- A minimum of 40% speech recognition in the Freiburg Monosyllables test in quiet at 65 dB SPL (at the last time tested)
- Fluent in German (the language of the test centre)
- Signed and dated ICF before the start of any study-specific procedure.

